Subsequent to the above-mentioned phase 1 study, a prospective longitudinal phase 2 study was initiated to evaluate the use of Gravid Ovipositing Sticky (GOS) trap and the NS1 testing system for surveillance of dengue virus transmission in urban Malaysia over a two-year period. The findings showed that dengue cases would occur lag one week after infected mosquitoes are obtained and will peak at lag of 2 to 3 weeks (30). These results showed that this proactive strategy is beneficial for dengue vector surveillance programme. The usage of the GOS trap which is simple to setup, cost effective (below USD 1 per trap) and environment friendly (i.e. use recyclable plastic materials) to capture *Ae. aegypti* followed by a rapid method of detecting of dengue virus using the NS1 dengue antigen kit has shown promising results. Control measures could be initiated when positive mosquitoes are detected, for example activity such as search and destroy breeding containers. This innovative usage of GOS trap coupled with NS1 detection in mosquito provides a comprehensive early warning and surveillance system that has the predictive capability for epidemic dengue.

6. Relevance to Government Policy, if any

This cluster randomised trial is expected to provide robust estimates of the intervention effects. A rigorous evaluation of these vector control interventions is vital to the development of an evidence-based control strategy and to help direct government resources in the right direction to reduce dengue epidemics.

7. Methodology

This is a community-based study assessing the knowledge, awareness and practice on dengue infection and its prevention. We choose PJU10 because it is the dengue 'hotspot' area according to local health council. We have identified a low-cost housing area with population of approximately 48700 people.

Sample size calculation:

Sample size for intervention trial:

To test for effectiveness of intervention in reducing dengue cases, on average, each housing unit will have 2% risk of dengue per year. A sample of 5710 unit (2855 per arm) will be required to achieve 80% power at alpha of 0.05 with the assumption of reduction in 50% of risk at the end of intervention. Eight apartments with 7979 residential units will be selected and randomised into intervention and control. Apartment will be the item of randomisation.

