All clusters in intervention arm will receive the GOS traps. A maximum of 21 traps will be set per apartment block, on every third floor. The traps will be monitored weekly and the abdomen of *Aedes* obtained will be tested for dengue virus using the NS1 antigen test kit. If positive search and destroy measures will be conducted by the community under the supervision of community leader and the health staff. To identify the mosquito which carries the virus, dengue NS1 antigen tests will be carried out from the head and thorax of the individual mosquitoes from positive pool of mosquitoes. For the control clusters, routine dengue control and surveillance will be carried out as per the current Ministry of Health control activity, where no traps will be set, and dengue control measure will be initiated when human cases are reported from the control group. Data collection will be conducted for 1 year and 6 months.

When a positive mosquito is obtained, flyers and banners will be distributed and hung to inform the residents of the presence of dengue transmission in the apartment block/apartment. Alternatively, the residents may also be approached house-to-house or an educational booth set up at strategic locations in the apartment to warn and educate the residents.

Phase III: Repeat of KAP questionnaire

The KAP questionnaire survey will be repeated 15 months after intervention in the intervention arm.

Phase IV: Statistical Analyses

Data of serologically confirmed dengue cases (by NS1 or IgM/IgG) from the eight residential blocks will be obtained from the Selangor State Health Department, Malaysia. It is mandatory for all hospitals and private practitioners to report cases to the Ministry of Health. The date of onset of case will be used for all data analyses.

For analysing the change in level of dengue KAP, the mean of the percentage score of the population for each domain (knowledge & attitude/practises) will be determined for the pre- and post-questionnaire. Then, paired t-test will be performed to determine the presence of significant changes in both means. A p-value of at most 0.05 indicates a significant change/improvement in the mean score (An increase in score percentage indicate a better outcome). Additionally, an individual percentage score of 80% and above indicates good knowledge/attitude/practice. Accordingly, chi-squared test will be used to determine the extent to which good knowledge is related to good attitudes/practises

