All statistical analyses will be done using weekly data and R programming language for statistical analysis (version 3.2.4) (30). The family of distributed lag non-linear models (DLNM), (*DLNM* package version 2.20), which can simultaneously analyse non-linear factor-response dependencies and delayed effects, and provides an estimate of the overall effect in the presence of delayed contributions will be utilised. For dengue cases and its relation to dengue-positive *Aedes* pool, the model to be used will be: `glm(case ~ cb.total_aedes + cb.ns1positive + ns(time, 3) + woy, family = quasipoisson, data)` where `woy` = week of the year. Both the *Ae. aegypti* / *Ae. albopictus* trapped per week and cases per week at each apartment will be analysed by generalised linear mixed model (GLMM). Zero inflation and Poisson distribution were incorporated in the analysis. Differences in numbers of *Ae. aegypti* and cases between blocks and between floors were tested with Tukey's contrasts at $P = 0.05$.

References

1. Gubler, D.J., and Clark, G.G. (1995). Dengue/dengue hemorrhagic fever: the emergence of a global health problem. *Emerg Infect Dis* 1, 55.
4. Faria NR, da Silva Azevedo RS, Kraemer MU, Souza R, Cunha MS, Hill SC, et al. (2016). Zika virus in the Americas: Early epidemiological and genetic findings. *Science* 352(6283):345-9.

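### The weekly-count GLMM is zero-inflated Poisson with no stated allowance for overdispersion, so Tukey contrasts between blocks and floors may exceed 0.05, chiefly for mosquito counts

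*Combined protocol and SAP*

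**What the plan says.** Under Methodology, Phase IV (Statistical Analyses), the plan describes two count models.

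- The distributed lag model relates weekly cases to dengue-positive mosquito pools. Its code sets "family = quasipoisson", so the variance may exceed the mean.
- A generalised linear mixed model is to be used for weekly *Aedes* counts and weekly cases at each apartment. Its distribution is given in one sentence: "Zero inflation and Poisson distribution were incorporated in the analysis". The differences in *Ae. aegypti* numbers "and cases between blocks and between floors were tested with Tukey's contrasts at" P = 0.05.

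For the mixed model the plan gives no random-effects structure, dispersion parameter, overdispersion check or fallback. Neither model comes with a count mean, a variance or a dispersion estimate.

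**The concern.** A zero-inflated Poisson mixes a point mass at zero with a Poisson. It can reproduce a surplus of empty weeks, but within the Poisson part the variance is tied to the mean. Weekly trap catches, and cases during an outbreak, may be clumped among the non-zero weeks as well. The model then understates the standard errors of block and floor effects.

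A random intercept for apartment would not cure this, because it does not describe week-to-week clumping within an apartment. What is at stake is the error rate of the planned pairwise tests: blocks or floors could be reported as different when they are not. The quasi-Poisson choice for the lag model shows that extra variance in cases was thought possible.

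**Working it through.** **Inputs from the documents**

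- Follow-up: "Data collection will be conducted for 1 year and 6 months", taken as 78 weekly counts per block.
- Case rate: the sample size section says "each housing unit will have 2% risk of dengue per year", with 7979 units in eight apartments. This gives 0.02 × 7979 / 8 / 52 = 0.38 cases per apartment per week.
- Stated level of the contrasts: 0.05.

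**Assumed, because the documents give no figure:** the mean trap count, the negative binomial k (variance = m + m²/k, so smaller k means more clumping) and the share of structural zeros.

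**Step 1: the stated level.** Data were simulated from a true zero-inflated Poisson: four blocks, 78 weeks, no block difference, 20% structural zeros, 400 runs per setting. The Tukey family-wise error was 5.0%, 4.8% and 4.5% at count means 0.5, 2 and 8. The planned method holds 0.05 when its distribution is right.

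**Step 2: the mechanism by hand.** Take negative binomial counts with mean m = 5 and k = 1.

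- Share of zeros: (k/(k+m))^k = 1/6.
- Mean of the non-zero counts: 5/(5/6) = 6.
- Their variance: (m + m²/k + m²)/(5/6) − 6² = 55/(5/6) − 36 = 30.
- The zero-inflated Poisson matches the non-zero mean: λ/(1 − e^−λ) = 6 gives λ = 5.985. It then implies a variance of 6 × (1 + 5.985 − 6) = 5.91.
- Variance ratio: 30/5.91 = 5.08. Standard errors are too small by √5.08 = 2.25.
- Approximate type I error: P(|Z| > 1.96/2.25) = 38%.

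The same steps give 14% (mean 2, k 2), 21% (mean 2, k 1), 27% (mean 5, k 2) and, at 0.38 cases per week with k 1, 8%.

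**Step 3: simulation of one two-block contrast.** Both blocks have the same true mean, with 78 weeks each, negative binomial data and no random effects. The test was at 5%, by Wald or likelihood ratio. Where a range is shown, it spans separate runs.

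| Mean per week | k | Zero-inflated Poisson | Negative binomial |
|---|---|---|---|
| 2 | 2 | 11–12% | 5% |
| 2 | 1 | 18–22% | 5–6% |
| 5 | 2 | 25–28% | 4–6% |
| 5 | 1 | 36–39% | 4–6% |
| 0.38 (cases) | 2 | 5% | 5% |
| 0.38 (cases) | 1 | 6–9% | 4% |
| 0.38–0.40 (cases) | 0.5 | 6–10% | 5–6% |

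With 600 runs the Monte Carlo standard error near 5% is √(0.05 × 0.95/600) = 0.9 points.

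**Step 4: family-wise error of the full Tukey set.** The design is that of step 1, but with overdispersed non-zero counts and no random effects.

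| Mean of count part | k = 4 | k = 2 | k = 1 |
|---|---|---|---|
| 0.5 | 5.3% | 6.3% | 8.5% |
| 2 | 11.8% | 17.5% | 35.0% |
| 8 | 44.8% | 63.0% | 77.5% |

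For cases (eight apartments, mean 0.38, 200 runs) the error was 5.5% at k 2, 3.5% at k 1 and 9.5% at k 0.5.

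**Step 5: do the remedies work?** A zero-inflated negative binomial gave family-wise error of 7.3% (mean 2, k 2), 9.0% (mean 2, k 1), and 5.5% at mean 8 for both k 2 and k 1. A zero-inflated Poisson with an observation-level random effect gave 4.0% and 4.7% at mean 2 (k 2 and k 1; 150 runs each). Both remove most or all of the excess.

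**The case against.** The strongest reply is that the simulated model is not necessarily the planned one. The plan specifies a mixed model, and the fits in steps 3 and 4 had no random effects. Week, trap or observation-level effects are usual in such models and can absorb the extra variance; step 5 shows that an observation-level effect does. This stands: it is not established that the planned analysis ignores overdispersion, only that no allowance is stated. It does not remove the point, because the error rate then depends on a term the plan never mentions.

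Second, the means and k are assumed. This also stands. A reader might infer that block and floor differences will be declared significant too often. The documents do not support that, since they give no dispersion, and at the protocol's own case rate the inflation is slight.

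Third, a reader might infer false precision in the comparison of intervention with control. The documents do not support this either. Phase II sets no traps in control clusters, so trap counts have no between-arm test. Only cases can be compared. A check with eight apartments (four per arm assumed), mean 0.38 and an apartment random intercept of SD 0.3 (assumed) gave null rejection rates, zero-inflated Poisson against negative binomial, of 7.3% against 7.7% (k 1) and 12.7% against 9.0% (k 0.5; standard error about 1.9 points). With no overdispersion both gave 11.9%. At most there is a hint at k 0.5.

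Last, the block and floor contrasts are not presented as the test of the intervention. That limits the weight of the point, but they are planned tests with a stated level.

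**Conclusion.** The concern holds in conditional form. The plan specifies a zero-inflated Poisson for the weekly counts and states no allowance for overdispersion among non-zero counts, while its own lag model for cases makes one.

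If trap counts have moderate or high means and are clumped, and no week- or observation-level effect absorbs this, the contrasts are liable to exceed 0.05. For a single two-block contrast the error is about 11% to 36% at means 2 to 5 and k 2 to 1 (up to 39% in repeat runs), against about 5% under a negative binomial. For cases at 0.38 per apartment-week it is about 7% to 8% for k 1 to 0.5 (6% to 10% across runs). No effect on the arm comparison is shown.

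These figures assume gamma-distributed extra variance and independent weeks; serial correlation was not modelled. Floor contrasts were not simulated separately. The mechanism is the same, but counts per floor are smaller than per block, so the inflation may be less.

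**What to change.** In Phase IV, replace the sentence on the distribution with a specification that does four things:

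1. Uses a negative binomial for the mixed-model counts, or a Poisson with an observation-level random effect.
2. Keeps a zero-inflation part only if it improves fit by a stated criterion.
3. States the random effects and reports residual dispersion.
4. Computes Tukey's contrasts from that model.

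The cost is a few lines of SAP text and a different family or one extra random term in the analysis code. The downside is wider intervals for block and floor differences where counts are overdispersed. The change does not deal with correlation between successive weeks, which is a separate matter.
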